REPETITIVE TRANSCRANIAL MAGNETIC STIMULATION (RTMS) FOR OBSESSIVE-COMPULSIVE DISORDER (OCD)

Regulatory Sponsor (S-I): [name], PhD
Co-Investigator: [name]
Study Product: Brainsway™ cingulate coil (HAC coil)
Protocol Number: AAAQ8771

Study Summary

Title	Repetitive Transcranial Magnetic Stimulation (TMS) for Obsessive-Compulsive Disorder (OCD)
Short Title	rTMS for OCD
Protocol Number	Initial version
Methodology	Open-label study to investigate the feasibility and effectiveness of administering rTMS to patients suffering from OCD.
Study Duration	Study duration will be 3 weeks
Study Center(s)	Single-center
Objectives	The goal of the study is to assess whether repetitive transcranial magnetic stimulation (rTMS) can be used as a non-invasive option to benefit patients suffering from Obsessive Compulsive Disorder (OCD)
Number of Subjects	15
Diagnosis and Main Inclusion Criteria	Obsessive-compulsive disorder
Study Product and Planned Use	Brainsway™ HAC-coil to target the cingulate cortex
Reference therapy	N/A
Statistical Methodology	Statistics will be computed to observe changes within subjects and between subjects to assess the effectiveness of rTMS

1 Introduction

1.1 Background

With a prevalence of nearly 3%, obsessive-compulsive disorder (OCD) is one of the most common psychiatric disorders in the US (1). Its clinical manifestation includes persistent, intrusive and irrational thoughts, such as obsessions, and repetitive behaviors, i.e., compulsions, that cause distress and impairment for the individual (2). From an international perspective, the WHO has reported that OCD accounts for approximately 1% of global years lost due to disability (1). Thus, it is a disease with notable socioeconomic impact both on a national and global scale.

The first line of treatment for OCD comprises pharmacotherapy with serotonin reuptake inhibitors (SRIs) and cognitive behavioral therapy (CBT). Although adherence to these therapies has been shown to improve symptoms in at least half of patients, 30-40% have residual symptoms (3) and 10-15% are refractory to standard therapies (4). Options are limited, but do exist for treatment-refractory patients or individuals with residual symptoms. Although the mechanisms of action are not fully understood, deep brain stimulation (DBS) (5, 6) and stereotactic lesions (7, 8) represent two invasive interventions that have shown promise in alleviating residual or refractory OCD symptoms.

However, transcranial magnetic stimulation (TMS) may offer an alternate, less-invasive therapy. Repetitive TMS (rTMS) has been the most studied non-invasive modality in the OCD population, and preliminary data

demonstrate varying degrees of success (9). rTMS hyperpolarizes and depolarizes targeted brain regions by delivering magnetic current through a coil (10-11).

The symptoms of OCD are a result of generalized deficits in cognitive control, defined as the processes that enable pursuit of a goal while overcoming strong, automatic competing influences (12). Response inhibition is an executive cognitive process and one aspect of cognitive control that has been shown to be deficient in OCD patients (13-15).

The dorsal anterior cingulate cortex (dACC) and its associated neurocircuitry play an important role in cognitive control. Neuroimaging studies (fMRI and PET) have shown the dACC to be hypermetabolic in individuals suffering from OCD (16-25). The inputs to and projections from dACC suggest that it may be a cognitive control “hub,” such that it would integrate incoming signals and in effect weigh the costs and benefits of exerting control, termed expected value of cognitive control (12). There is evidence to support this putative role for dACC at the level of neuroanatomy, neurophysiology, and functional imaging (26-29). Deficient fear extinction may also be present in patients with OCD as demonstrated by studies showing decreased activation of dACC in fMRI during fear conditioning tasks (30). Finally, it has also been observed that OCD individuals are less quick to change behavior after making a mistake on a task, and such cognitive inflexibility is associated with altered fMRI activation of dACC and other cortical areas (31-32).

Electroencephalography (EEG) can be used to measure event-related potentials (ERPs) associated with cognitive control signals. Specifically, error-related negativity (ERN) signals that have been localized to dACC (33), are produced during tasks that involve cognitive control (34), and have been found to have increased amplitude in OCD patients, perhaps reflecting overactive error monitoring (35-37). Evidently, increase in the “frontal midline theta” power correlates with clinical measures of anxiety and conflict (34).

To summarize, rTMS can serve as a promising neuromodulatory intervention to manage refractory and residual symptoms associated with OCD. It can non-invasively target dACC, the putative “hub” for the cognitive processes, i.e., cognitive control, that are deficient in OCD patients. The present proposal is aimed at examining the effect of rTMS delivered with an H1 coil at the dACC on neurophysiological activity during a cognitive control task, as measured with fMRI and EEG.

1.2 *Investigational Device*

The coil used in the study to apply rTMS is an H1-coil geometry manufactured by Brainsway™, specifically to target the cingulate cortex (HAC, Brainsway™ cingulate coil). The design of the coil is patented and aimed to induce stimulation at deeper regions without over-stimulating facial nerves or other superficial cortical regions. While not approved for OCD yet, the H-coil has received an IDE for cocaine addiction and was IDE exempt for marijuana addiction. The rTMS coil includes a flexible base shaped to fit the human head. The base is optimally fitted to the scalp at the desired region. This coil will be used in conjunction with a Magstim Rapid Stimulator (Magstim Company Limited, Whitland, UK).

1.3 *Preclinical Data*

The abnormal neural circuitry that exists in OCD involves a relative decrease in glutamatergic signaling and grey matter within the dACC compared to healthy controls. rTMS has been explored as a method of treatment for cases of OCD that are refractory to medical treatment. Rupp et al used a rodent model to discern the pattern of brain activation after subjecting the animals to rTMS. The researchers used a round coil to deliver 25-Hz pulses for 2 seconds, then euthanized and decapitated the animals 45-60 minutes later to examine their brain tissue. They found that the rats subjected to rTMS had increased c-fos expression in the cingulate, primary and secondary motor cortices, suggesting that these areas were selectively stimulated by rTMS. Expression was greatest in the ACC. This shows promise for targeting the dACC in OCD patients (38). Several OCD animal models have demonstrated that applying high frequency stimulation to certain areas of the brain, such as the subthalamic nucleus and the nucleus accumbens, can decrease compulsive behavior. Kupsch et al subjected quinpirole-induced rats to high frequency stimulation (130Hz) to functionally inhibit the subthalamic nucleus and observed significantly

decreased compulsive checking behavior (39). Winter et al later applied the same high frequency stimulation to the nucleus accumbens via deep brain stimulation and also observed significantly decreased compulsive checking (40). It can be inferred that applying similar electrical stimulation to modulate dACC circuitry may also yield significant reductions in the severity of OCD symptoms.

1.4 Clinical Data to Date

An initial feasibility study was conducted with the Brainsway™ H1-coil at the NIH on 6 healthy volunteers. The device was determined to be non-significant risk (NSR) and therefore, the trial was conducted under an IRB approval. Another safety study was conducted in 2005 at the Shalvata Mental Health Center, Hod Ha Sharon, Israel. The study compared H1-coil, H2-coil, standard figure-8 coil and a sham coil in healthy subjects. Additionally, Brainsway™ has also conducted a clinical study for the indication of MDD. This study is summarized in their IDE and a recent publication (41).

The aforementioned pilot and feasibility studies confirm the safety profile of the coil. It should be noted, that the parameters that will be employed in our OCD study, while different from those of the MDD study, comply with the safety guidelines recommended by the manufacturer.

1.5 Research Risks & Benefits

1.5.1 Risk of Investigational Device

The risks of rTMS include seizures, headaches, and hearing problems. Since the rTMS induces an electrical field on the brain, the most serious risk is the possibility of having a seizure.

The rTMS coil that is being used in this study is called the "HAC coil". While rTMS has been approved by the FDA for some neuropsychiatric indications such as MDD, this particular coil is experimental and has not yet been approved by the FDA for OCD. Seizures from any kind of rTMS treatment are rare and occur at a rate of about 2/1000. In people who received rTMS in the past with similar intensity and the same Hcoil we will be using in this study, three out of more than 200 people had a seizure. Patients experiencing adverse effects were on certain medications that made them more prone to seizures. In order to minimize the risk for seizures, patients will not be able to participate in this study if they have a medical or psychiatric condition that requires them to take certain medications regularly. Patients will also not be allowed to participate if they have a family history of seizures. A physician will be present during each rTMS treatment and will provide necessary care in case of adverse events. Additionally, suicidal ideation and emergence of manic symptoms following rTMS treatment are also potential risks. Should any of these occur, patients will not be able to continue with the remainder of the study.

There is also a risk of hearing problems (hearing loss or ringing in the ears) after rTMS. This problem is less likely to occur with the proper use of earplugs. The most common risk of rTMS is the possibility of having a headache after the sessions. Over the counter pain medicines (like ibuprofen or acetaminophen) can be taken if needed. Additional risks include scalp and dental pain, which can be treated with over the counter pain medications also. In case of any other adverse events, rTMS will be stopped and patient will be monitored closely.

1.5.2 Other Risks of Study Participation

While there have been no reports of any harmful long-term effects caused by the MRI scanner, including magnets of high strength, the long-term effects of being placed in a magnet of the strength used in this study are unknown. Although there are no known risks associated with pregnancy, females cannot participate in this study if pregnant. A negative pregnancy test (urine analysis) is required at the time of screening as well as the day of the fMRI scans.

Some people have reported sensations during MRI scans, such as "tingling" or "twitching" (or, very rarely, a painful sensation), which are caused by changes in the magnetic field that can stimulate nerves in your

body. With any MRI scan, on occasion, some people experience nervousness or discomfort due to the scanner's small space and the need to lie still. Except for pacemakers, some types of metallic implants, and medication patches, we are not aware of any other potentially dangerous interactions or hazards associated with the MRI scan. The MRI scanner also produces a loud noise; earplugs will be provided to reduce this discomfort. It may be uncomfortable to lie motionless in the scanner, and it may cause the patient to feel anxious. A member of the research staff will be available to provide support.

The only risk associated with psychological testing and behavioral assessment is potential nervousness/frustration with the tasks. The research team will thoroughly explain the tests and will be available to answer questions that may arise during tasks.

1.5.3 Potential benefits

Throughout the course of the study, rTMS may decrease symptoms associated with OCD. rTMS may also ease the patient's ability to engage in cognitive behavior therapy (CBT), which may also help control their symptoms. However there is a possibility of no therapeutic effect for OCD, and therefore there might be no direct benefit to the patient.

As a benefit to the OCD patient cohort, neuroimaging during this study will be used to evaluate rTMS as a screening procedure to help determine which patient populations might derive the most benefit from currently implemented invasive treatment options such as cingulotomy or DBS. Likewise, findings from neuroimaging and EEG will also add to our knowledge of the circuit involved in OCD by assessing acute and longitudinal biomarkers.

2 Study Objectives

The purpose of this study is to understand how rTMS might best benefit patients suffering from disorders of the dACC. In particular, we will determine how rTMS affects patients with OCD. We also aim to evaluate rTMS as a screening procedure to help determine which patient populations might derive the most benefit from currently implemented invasive treatment options such as cingulotomy or DBS. Lastly, we will study how neuromodulation affects the circuitry of the brain by assessing acute and longitudinal biomarkers from neuroimaging.

3 Study Design

3.1 General Design

rTMS delivery: High-frequency (10 Hz) deep TMS will be administered at the dACC to patients over 3 weeks using the HAC-coil (Brainsway™ cingulate coil) designed specifically to target the cingulate cortex and the Magstim Rapid stimulator (Magstim Company Limited, Whitland, UK). Sessions will be administered five times a week with a total of 15 visits. The intensity of stimulation will be relative to resting motor threshold (110%). Forty 3-second trains with an inter-train period of 20 seconds will be applied. Total number of pulses administered will be 1200. Periodic weekly behavioral assessments will be performed with the Yale-Brown Obsessive Compulsive Scale (Y-BOCS) to monitor OCD symptoms. We will also test for suicidal ideation (C-SSRS) and monitor manic symptoms (YMRS) twice a week in addition to baseline and at the end of treatment course (x 8 total) and test cognitive function with Minimental status examination (MMSE). Subjects will be compensated for their daily visits in order to offset inconvenience related to time, effort and transportation costs. They will receive \$100 per fMRI session (x2 total) plus \$40 per TMS session (x15 total) over the study period.

Neuropsychological scales and tests: Neuropsychological evaluations will be administered at baseline and at the end of the study.

1. Scales (expected to take 30-40 minutes total):

- USP-Sensory Phenomena Scale

- Hamilton Depression Rating Scale
- Hamilton Anxiety Rating Scale
- Beck Anxiety Inventory
- Beck Depression Inventory, 2nd Edition
- Sheehan Disability Scale
- Barratt Impulsiveness Scale (BIS -11)
- Clinical Global Impression (CGI)
- Quality of Life Enjoyment and Satisfaction- short form (Q-LES)

2. Neuropsychological measures (expected to take about 90 minutes and can be performed in separate sessions as needed):

- Wechsler Abbreviated Scale of Intelligence (WASI)
- WMS-III Faces, LM, Digit Span, Spatial Span, LNS
- Rey Osterrieth Complex Figure (ROCF)
- California Verbal Learning Test, 2nd Edition (CVLT-II)
- Iowa Gambling Test (IGT)
- Wisconsin Card Sort Task (WCST)
- Judgment of Line Orientation
- Boston Naming Test
- DKEFS Verbal Fluency, Trails, Color Word Interference Test
- Grooved Pegs

Multi-Source Interference Task (MSIT): We will use the multi-source interference task (MSIT) to engage the dACC and study cognitive control in OCD. The MSIT combines elements of Simon and Erickson flanker tasks. A 3-number cue is presented to the subject on a screen. Of the three numbers, 2 are the same and represent 'distractors'. The unique different number is the 'target'. The patient is instructed to press the button corresponding to the 'target' number (left button if the target is '1', middle if '2', right if '3'). Importantly, the subject should push the button corresponding to the target regardless of where that target is in the sequence. Four levels of conflict are presented:

- 1) No conflict: Distractors are absent and target is in correct spatial location (ex: 020)
- 2) Flanker Interference: Distractors present and target is in correct spatial location (ex: 121)
- 3) Spatial Interference: Distractors are absent, but target is not in correct spatial location (ex: 200)
- 4) Both Interference: Distractors are present and target in not in correct spatial location (ex: 211)

Behavior will be quantified based on response accuracy and reaction time during the task. These results will be correlated with changes in Y-BOCS and changes in neuroimaging to determine the effect of rTMS on cognitive control in OCD.

Simultaneous fMRI/EEG scans along with structural and diffusion MRI will be acquired at the beginning and end of treatment protocol. Pre and post-TMS EEG will also be collected 2 times a week.

Neuroimaging and Neurophysiology: High resolution (3T) structural MRI will be acquired along with DTI at the beginning and completion of treatment. Also, a simultaneous fMRI-EEG (40 channels) scan will be acquired at these times while the patient is completing the MSIT. An EEG-based fMRI analysis will help us overcome limitations of spatial and temporal resolution that are evident when using either technique alone. A data-driven approach will be used to identify temporally specific and task-relevant projections of the EEG data, which will then be used to construct fMRI regressors. This approach will allow us to link BOLD correlates with task engagement, which is not possible with traditional acquisitions. Further, it will enable us to study trial-to-trial variability as we can measure both the amplitude and variance of the ERPs.

Additionally, pre-rTMS and post-rTMS high-density scalp EEG data (128 channels) will be acquired two times a week for a total of 12 EEG acquisitions. The patient will be engaged in the MSIT during EEG acquisitions. EEG analysis will be used to quantify acute effects of rTMS by exploring within-session data,

and longitudinal effects of rTMS by exploring between-session data. The high-density acquisition will also allow for a thorough analysis in sensor and source domains.

Data Analysis: fMRI regressors will be constructed at multiple offsets in the epoched EEG data to view the temporal progression of the discriminating components (Walz 2013). Linear classifiers will be trained on EEG data to estimate a set of spatial weights to maximize discrimination of 2 conditions. Regressors will also account for single-trial variability. Lastly, we will compute ICA-based source localization on the fMRI data to extract the nodes of the underlying network evoked during this task.

For the EEG analysis, we will first analyze the data in sensor domain and assess the effect of rTMS by computing differences in ERPs and midline frontal theta. This initial analysis will then be used to reconstruct source signal. Region-specific measures (power) and connectivity measures (frequency-dependent coherence) will also be computed. Although EEG measures correspond to a fraction of total synaptic action in a particular tissue volume, strong correlations have been reported between cognitive processing and event-related potentials that occur due to interactions with background synaptic action fields. Therefore, by extending our measures from source activity to source connectivity, we can indirectly measure changes in synaptic plasticity.

Each patient will serve as their own control and statistical comparisons will be made between measures at baseline and at the end of the TMS protocol (3 weeks). Although this study design doesn't address time-effects, we believe it is a crucial first step towards a better understanding of the effects of TMS.

Effectiveness Variables:

- 1) Changes in midline frontal theta and ERPs will be compared pre and post rTMS for OCD
- 2) Changes in dACC connectivity with frontal regions (DLPFC and OFC) will be assessed over the course of rTMS treatment for OCD
- 3) Changes in YBOCS will be assessed over the course of rTMS as a measure of secondary effectiveness. Clinical response will be defined as 35% reduction in YBOCS from baseline.

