5.4.2 Storage

The stimulation set-up is currently housed at the New York State Psychiatric Institute on the third floor. Trained investigators or physicians will have access to the setup and will administer the stimulation. A physician will be present during rTMS sessions to ensure patient safety.

6 Study Procedures

	Monday	Tuesday	Wednesday	Thursday	Friday
Baseline	Neuroimaging, Neurophysiology and Neuropsychiatry evaluations				
Week 1	rTMS	rTMS preTMS EEG postTMS EEG MMSE, YMRS,CGI, CSSRS	rTMS	rTMS preTMS EEG postTMS EEG YBOCS, MMSE, YMRS, CGI, CSSRS	rTMS
Week 2	rTMS	rTMS preTMS EEG postTMS EEG MMSE, YMRS, CGI, CSSRS	rTMS	rTMS preTMS EEG postTMS EEG YBOCS, MMSE, YMRS, CGI, CSSRS	rTMS
Week 3	rTMS	rTMS preTMS EEG postTMS EEG MMSE, YMRS, CGI, CSSRS	rTMS	rTMS preTMS EEG postTMS EEG YBOCS, MMSE, YMRS, CGI, CSSRS	rTMS
Follow-up	Neuroimaging, Neurophysiology and Neuropsychiatry evaluations				

7 Statistical Plan

Statistical analyses with time series data and factor analysis will be carried out both within subject (to assess reliability of the observed effects across trials) and across subjects (to assess the generalizability across participants). Sample sizes are chosen based on expected effect sizes and the large heterogeneity in this subject population.

8 Safety and Adverse Events

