9.1 Confidentiality

Information about study subjects will be kept confidential and managed according to the requirements of the Health Insurance Portability and Accountability Act of 1996 (HIPAA). All study data will be coded with a unique alphanumeric identifier. The coded data will be stored on an end user device protected by a strong password. The key will be stored in an encrypted spreadsheet on an end-user device belonging to the primary investigator. All paper documents, including outcome measurement tools, consent and HIPAA forms will be maintained in a locked file cabinet. We will collect the minimum amount of information necessary for the purposes this study. Only approved study personnel will have access to this data, and all of the information gathered will be used for this study unless data has clinical relevance to the patient's treatment, in which case it will be shared with the patient's clinical team.

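### EEG and fMRI processing is not masked to time point, and EEG source choices are not stated to be independent of the observed pre/post difference

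*Combined protocol and SAP*

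**What the plan says.** The Study Summary describes an "Open-label study to investigate the feasibility and effectiveness of administering rTMS" and gives no reference therapy. Section 3.1 compares each patient with their own baseline at three weeks.

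The Data Analysis part of Section 3.1 puts the EEG work in sequence. The sensor-domain step comes first and is to "assess the effect of rTMS by computing differences in ERPs and midline frontal theta". The next sentence reads "This initial analysis will then be used to reconstruct source signal". Regional power and coherence-based connectivity are also to be computed.

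The Effectiveness Variables in Section 3.1 list the change in midline frontal theta and ERPs first. The change in dACC connectivity with DLPFC and OFC comes second, without saying whether it is measured by EEG or fMRI. Y-BOCS is third and is called secondary.

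The only rule on coding data is in Section 9.1, Confidentiality: "All study data will be coded with a unique alphanumeric identifier". It does not mention visit, session or pre/post status. Section 7 (Statistical Plan) names time-series and factor analysis, and fixes no windows, bands, artifact rules or regions.

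**The concern.** Treatment cannot be masked in a single-arm open-label study, but the processing of recordings can be masked to time point. EEG and fMRI processing normally involves judgement: which trials to reject, which components to keep, which ERP window, theta limits and electrodes to use, and where to place sources. An analyst who knows which files are post-treatment can lean in these choices without intending to. There is no comparison arm in which a similar lean could cancel, so all of it would go into the pre/post contrast and look like an effect of rTMS.

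The order of the EEG steps adds a second route. If windows or sources are chosen after the sensor-level difference has been seen, and partly because of it, testing the same difference there on the same data no longer has its nominal error rate.

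At stake are the two variables the protocol lists ahead of the clinical scale.

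**Working it through.** **Inputs from the protocol.** 15 patients (Study Summary); three weeks, two EEG days per week, one recording before and one after stimulation on each of those days (Section 3.1 and the Section 6 schedule); two fMRI-EEG scans per patient (Section 3.1).

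**Assumptions, because the protocol gives no values.** A paired t-test at two-sided 5%; all 15 patients complete (14 degrees of freedom); the processing shift b, in SDs of the paired difference; the number K of candidate regions or windows; and the correlation between candidates.

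**Step 1: the protocol's own figures.** 3 weeks × 2 days × 2 recordings = 12, which agrees with "will be acquired two times a week for a total of 12 EEG acquisitions". The sample size of 15 cannot be reproduced: Section 7 says "Sample sizes are chosen based on expected effect sizes and the large heterogeneity in this subject population" but states no effect size, SD, error rate or power. The recordings exposed are 15 × 12 = 180 scalp EEG and 15 × 2 = 30 fMRI-EEG, 210 in all.

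**Step 2: the text.**
- *Masking.* No section describes hiding time point from those who process the data. Section 9.1 is the only coding rule, and its stated purpose is confidentiality.
- *EEG sequence.* The rTMS difference belongs to the sensor-level step, and that step feeds source reconstruction. What is carried forward is not stated.
- *fMRI.* Regressors come from EEG classifiers separating two unnamed conditions, and ICA extracts the network evoked by the task. Nothing links these choices to the pre/post difference.

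**Step 3: illustration of a processing shift.** With no true effect, a shift b gives a t statistic with noncentrality b√15, where √15 = 3.873. The rejection rate is P(|T| > 2.145) on 14 degrees of freedom.

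| b (assumed) | Noncentrality | Rejection rate |
|---|---|---|
| 0 | 0 | 5.0% |
| 0.1 | 0.387 | 6.5% |
| 0.2 | 0.775 | 11.2% |
| 0.3 | 1.162 | 19.2% |
| 0.5 | 1.936 | 43.8% |

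**Step 4: illustration of selection on the contrast.** Suppose the candidate with the largest observed difference is chosen and tested uncorrected. With K independent candidates the type I error is 1 − 0.95^K. With correlation 0.8 it was simulated (40,000 runs of 15 pairs).

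| K (assumed) | Independent | Correlation 0.8 |
|---|---|---|
| 2 | 9.8% | 7.8% |
| 5 | 22.6% | 13.0% |
| 10 | 40.1% | 18.3% |

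**Step 5: why pooling helps.** Cov(pre + post, post − pre) = Var(post) − Var(pre). If each recording has equal weight and the two variances are similar, this is near zero. Choices made on the pooled signal then carry little information about the difference to be tested.

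**The case against.** A reader might infer several stronger things that the documents do not support.

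- *That the plan has the pre/post difference steer source reconstruction.* This is a natural reading, but Section 3.1 does not say what is carried forward. It could be only cleaned data, epochs, bands or windows. What can be said is that independence from the contrast is not stated.
- *That the coding hides patient identity and nothing else.* Section 9.1 does not say whether the identifier is per patient or per recording. It simply does not mention time point.
- *That fMRI is steered in the same way.* The sequence sentence concerns EEG. The fMRI text points to task contrasts, although the two conditions are not named.
- *That everything is left open.* Variable 1 already specifies midline frontal theta, and variable 2 already names dACC, DLPFC and OFC. Exact windows, band limits, electrodes and region definitions are what is missing. Trial rejection and component selection are usual steps that the protocol does not describe.
- *That the rejection rates estimate harm.* They show only what an assumed bias would do. The effectiveness variables are worded as changes without direction. The Background does report raised error-related signals in OCD, so an analyst could hold an expectation, but that does not establish the direction of a bias.

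A further fair objection is one of priority. This is a 15-patient feasibility study whose EEG work is partly exploratory, and Section 3.1 concedes that time effects are not addressed. Masked processing would still leave the pre/post change open to other explanations. That stands, and it limits the weight of the point. It does not remove it: the concession covers time effects, not analyst choices, and the latter can be reduced without adding an arm.

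**Conclusion.** The point holds as an inexpensive improvement. The protocol describes no masking of EEG or fMRI processing to time point. For EEG, it computes the sensor-level difference before source reconstruction without stating that later choices are independent of that difference. Variable 1 is exposed to both routes, and so is variable 2 where it rests on EEG sources. The fMRI measures are exposed only through the absence of masking.

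The size and direction of any bias cannot be derived from the documents. The rates of 11% to 44% for shifts of 0.2 to 0.5 SD, and of 8% to 40% for selection among 2 to 10 candidates, rest on assumed shifts, candidate numbers and correlations, a two-sided 5% paired test and 15 completers.

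**What to change.** Add to Sections 3.1 (Data Analysis) and 9.1:

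1. An existing team member who does not process the data gives every recording a random code that hides pre/post, session number and baseline/follow-up, and removes time stamps.
2. Artifact rejection, component selection, ERP windows, theta band and electrodes are decided and locked on the coded files, using data pooled over time points.
3. Source regions are those already named (dACC, DLPFC and OFC), defined from the pooled task response and not from the pre/post difference. The sentence linking the sensor analysis to source reconstruction is reworded to say so.
4. Only then are the codes opened and the differences computed.

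This must be in place before processing starts, because an analyst who has seen the labelled difference cannot be re-masked.

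The cost is low but not nil. If all 15 patients complete, about 180 scalp EEG and 30 fMRI-EEG recordings need relabelling. No pre/post results are available until processing is locked. Residual stimulation artifact may reveal some post-treatment files. The number of patients, the visits and the paired comparison do not change. Practice, time and patient-expectation effects remain, and the report should say so.
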